UPCR	Urine protein:creatinine ratio
WHO-DRL	WHO Drug Dictionary

1. INTRODUCTION

Immunoglobulin A nephropathy (IgAN) is the most common form of primary glomerulonephritis and can progress to renal failure.

The clinical presentation of IgAN is highly variable, ranging from asymptomatic microscopic hematuria to a rapidly progressive form of glomerulonephritis. The therapeutic options are limited and include nonspecific treatment to reduce blood pressure and proteinuria by renin-angiotensin system (RAS) blockade. No disease-specific therapies are currently available, and an unmet need persists for disease-modifying interventions.

Cemdisiran is an investigational RNA interference (RNAi) therapeutic designed to suppress liver production of complement component 5(C5) mRNA that is covalently linked to a triantennary N-acetylgalactosamine (Tri-GalNAc)

ligand, resulting in inhibition of terminal complement pathway activity and prevention of membrane attack complex (MAC) formation and C5a release. This inhibition would be expected to reduce mesangial cell proliferation and tissue injury in patients with IgAN, resulting in reduced renal injury. Both lectin and alternative pathways of complement have been implicated in IgAN pathology. Cemdisiran-mediated silencing of C5 will inhibit MAC formation and C5a release regardless of the activating pathway.

Study ALN-CC5-005 is a Phase 2 study to evaluate the efficacy and safety of cemdisiran in the treatment of patients with IgAN. This statistical analysis plan (SAP) has been developed based on the Protocol Amendment 4 dated 19 January 2021. Any change to the data analysis methods described in the protocol, as well as the justification for the change, will be described in the SAP (Section 8).

2. STUDY OVERVIEW

2.1. Study Design

This study is a multicenter, double-blind, placebo-controlled study comprised of three periods (Figure 1). Eligible patients will begin a 14-week observational run-in period during which treatment with the standard of care is expected to remain unchanged. At the end of run-in period, patients whose average urine protein (UP) of two valid urine collections is at or higher than 1g/24-h are eligible for randomization into the 36-week double blind (DB) period. Approximately 30 patients are planned to be randomized in a 2:1 ratio, 20 in the cemdisiran arm and 10 in the placebo arm in the DB period, which is followed by a 156-week open-label extension (OLE) period to further evaluate the long-term safety and efficacy. All patients will be followed for safety for 52 weeks after the end of study visit.

The independent Data Monitoring Committee (DMC) will have access to subject level treatment assignments and perform periodic reviews of unblinded data throughout. Details are provided in the DMC Charter of the study.

Figure 1 Study Design

days)	Run-in Period (14 Weeks)		Treatment 1 (36 Wee	Freatment Period (36 Weeks)		sment	Open-label Extension (156 Weeks)		iod	
Screening (up to 120 c	Standard of care	mization (2:1	ALN-CC5 600mg Q4W (n=20) + Standard of care)T k 32)	S ¢ 36)	ndpoint asses	ALN-CC5	DT (c 184) 0S (s 188)	SS (188)	ty Follow-up (2 Weeks)
		Rando	Placebo (n=10) + Standard of care	EC (Wee	EC (Wee	Primary e	+ Standard of care	EC (Week	EC (Week	Safe (5

2.2. Randomization Methodology

At the end of run-in period, patients will be randomized 2:1 to the cemdisiran or placebo arms upon confirmation of eligibility using the Interactive Response System (IRS), followed by vaccination against meningococcal infections. Randomization will be carried out by the permuted block randomization stratified by baseline urine proteinuria levels ($\geq 1g/24h$ and < 2g/24h versus $\geq 2g/24h$).

2.3. Blinding and Unblinding

Treatment assignments will be maintained by the IRS. Any unplanned unblinding to investigators or patients occurring during the 36-weeks DB placebo-controlled treatment period will be documented and reported in the Clinical Study Report (CSR).

During the DB treatment period, all subjects will be randomly assigned to cemdisiran or placebo. All site personnel and patients will be blinded to study drug during the DB period. Sponsor personnel will not be blinded to study treatment. Details regarding the blinding aspects during the study are outlined in a Randomization and Blinding Plan for ALN-CC5-005.

2.4. Study Procedures

The schedules of assessments are described in study protocol Table 1 for the DB period and study protocol Table 2 for the OLE period.

3. OBJECTIVE AND ENDPOINTS

The study objectives and endpoints based on the study protocol are presented Table 1 below.

Endpoints		
• Percent change from baseline in urine protein/creatinine ratio [UPCR] as measured in 24-hour urine at Week 32		
 Percent change from baseline in 24-hour proteinuria (g/24-hours) at Week 32 Percent of patients with partial clinical remission (urine protein [UP] <1.0 g/24-hour) at Week 32 Percent of patients with >50% reduction in 24-hour proteinuria at Week 32 		
 Change from baseline in UPCR as measured in spot urine at Week 32 Change from baseline in hematuria at Week 32 Erequency of adverse events (AEs) 		
• Trequency of adverse events (TES)		
 Change from baseline in estimated glomerular filtration rate (eGFR) at Week 32 The slope of eGFR computed for the first 36 weeks using all assessments during the period The slope of eGFR computed for the entire study period including the open label extension using all assessments during the study. Change from baseline in creatinine clearance at Week 32 Percent of patients in full clinical remission (Urine Protein [UP] <0.3 g/24-hour) at Week 32 		

Table 1Objectives and endpoints

Objectives	Endpoints		
• To assess the incidence of antidrug	• Change from baseline in the urine		
antibodies (ADA)	albumin/creatinine ratio (UACR) as		
	measured in 24-hour urine at Week 32		
	• Change from baseline in C5 level over		
	the course of the study		
	• Change from baseline in complement		
	activity (Complement Alternative		
	Pathway [CAP] and Complement		
	Classical Pathway [CCP]) over the		
	course of the study		
	• Evaluation of area under the curve		
	(AUC), maximum plasma		
	concentration (C_{max}) , time to		
	maximum plasma concentration		
	(T_{max}) , terminal half-life $(t^{1/2})$,		
	clearance (CL/F), volume of		
	distribution (V/F), cumulative amount		
	excreted unchanged in urine (Ae) and		
	percent of dose excreted in the urine		
	(fe) of cemdisiran (25-mer) and 23- mer		
	• Evaluation of AUC, Cmax, Tmax, t ¹ /2.		
	CL/F. V/F. Ae and fe of 22-mer		
	AS(N-1)3'		
	• Change from baseline in levels of		
	renal damage, complement activation		
	and inflammation markers over the		
	course of the study		
	• Incidence of antidrug antibodies		
	(ADA)		

4. **PATIENT POPULATION**

4.1. **Population Definitions**

The following patient populations will be used for analyses:

• Modified Intent-to-Treat Analysis Set (mITT): All patients who receive any amount of study drug and have baseline and at least one post-baseline 24-hour urine protein creatinine ratio assessment. Patients will be grouped by assigned treatments (i.e., as randomized).

- Safety Analysis Set: All patients who receive any amount of study drug. Patients will be analyzed according to the treatment actually received.
- PK Analysis Set: All patients who receive a full dose of study drug and have at least 1 PK concentration measurement.
- PD Analysis Set: All patients who receive a full dose of study drug and who have at least one post-dose blood sample for the determination of plasma C5 level.
- All Cemdisiran Treated Set: All patients who receive at least one dose of cemdisiran, including patients who take cemdisiran during the DB period and patients who first take placebo during the DB period and switch to cemdisiran during the OLE period.

The primary population used to evaluate efficacy will be the mITT Population unless stated otherwise. Safety will be analyzed using the Safety Analysis Set. The PK and PD Analysis Sets will be used to conduct PK and PD analyses, respectively. The All Cemdisiran Treated Set will be used to summarize long-term efficacy and safety of cemdisiran.

4.2. **Protocol Deviations**

Protocol deviations will be classified into major or minor deviations by medical review. A major deviation is defined as a deviation that may significantly impact the completeness, accuracy and/or reliability of the trial data; that may significantly affect a patient's rights, safety and wellbeing (ICH.E3 R1 Structure and Contents of Clinical Study Reports Guidance for Industry. 2013). Major protocol deviations will be reviewed and approved by Alnylam prior to the interim database lock for the primary analysis of the DB treatment period. All protocol deviations will be presented in a listing. The Sponsor or designee will be responsible for producing the final protocol deviations file. This file will include at a minimum each protocol deviation and whether or not this deviation is classified as a major protocol deviations. This file will be finalized prior to the primary treatment phase database lock. Protocol deviations will be summarized in the CSR.

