7. STATISTICAL ANALYSIS

7.1. Primary Endpoint

The primary endpoint of the study is the percent change from baseline in urine protein/creatinine ratio [UPCR] as measured in 24-hour urine at Week 32. The analysis will be conducted using the modified ITT analysis set.

Valid 24-hour urine protein values collected during the DB period will be included in the primary analysis (1 valid assessment at week 16 visit and the mean of two valid assessments at baseline and week 32 visit). All 24-hour urine samples need to meet the validity criteria below (Section 6.4.1.1 of the protocol). The 24-hour UPCR at baseline or Week 32 is the average of two valid collections.

A 24-hour urine collection will be considered valid if the following criteria are met:

- The collection is between 22-26 hours in duration between the initial discarded void and the last void or attempt to void.
- No voids are missed between the start and end time of the collection as indicated by the patient's urine collection diary.

The resulting 24-hour UPCR at each visit will be log transformed for analyses.[Fellstrom 2017; Li 2006] The primary analysis will be performed using a restricted maximum likelihood (REML) based Mixed-Effect Model Repeated Measures (MMRM) approach. The outcome variable is change from baseline in 24-hour UPCR in log-scale at week 16 and week 32 visits. Analysis will include fixed effects of treatment (cemdisiran vs. placebo), scheduled visits (week 16 and week 32), interaction term of treatment and scheduled visits, baseline 24-hour UPCR in log-scale (continuous), and patient as a random effect. Unstructured working correlation will be used to model the within-patient errors. If the fit of covariance structure fails to converge, independent correlation structure will be used. At each visit, least square (LS) means ($\hat{\mu}_j$) with corresponding standard errors (SEM) and 90% CI will be displayed by treatment arm. The primary comparison is the LS mean treatment difference (cemdisiran – placebo) in percent change of 24-hour UPCR at week 32 visit from baseline. This LS mean difference will be presented along with corresponding standard errors (SEMs), 90% CIs and p-value from the model.

The following results will also be presented:

• Placebo-adjusted geometric mean percent change at week 32 visit:

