7.1.1. Sensitivity Analyses

The first sensitivity analysis will be conducted to evaluate the robustness of the primary model using normality of log-transformed 24-hour UPCR data assumption. A stratified rank ANCOVA analysis [LaVange and Koch 2006] will be conducted without using the normality assumption of log-transformed 24-hour UPCR data. The following steps will be performed:

- 1. Standardized ranks within each stratification stratum will be derived across the two treatment groups for the baseline and the change from baseline at Week 32 in 24-hour UPCR
- 2. The linear regression model will be fitted separately for each stratum where the standardized rank of the change from baseline at Week 32 in 24-hour UPCR is the outcome variable, the standardized rank of the baseline is the only covariate
- 3. The stratified mean score test will be performed to compare the two treatment groups using the values of the residuals from the above model as scores and stratification factor as the stratum
- 4. Cochran-Mantel-Haenszel (CMH) p-value is obtained

The second sensitivity analysis is to assess the impact of missing data and the robustness of the primary analysis. The analysis will use the same MMRM model on the imputed data, of which the missing 24-hour UPCR value will be imputed with the spot UPCR [Ginsberg 1983; Viswanathan and Upadhyay 2011] assessed closest to the date of missing value, when available. Depending on the extent of missing values this sensitivity analysis might not be needed.

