7.2. Secondary Endpoints

For secondary endpoints assessed in DB period, the analysis will compare randomized arms (cemdisiran vs. placebo) using the mITT analysis set.

The secondary endpoints which are assessed beyond Week 36 will be summarized to describe the long-term efficacy of cemdisiran using the All Cemdisiran Treated Analysis Set by treatment sequence, i.e., cemdisiran/cemdisiran, placebo/cemdisiran, and All Cemdisiran.

The planned analyses of the secondary endpoints are summarized in Table 2.

Endpoint	Statistical Method	Notes
Percent of patients with partial clinical remission (urine protein [UP] <1.0g/24-hour) at Week 32	Treatment comparison will be conducted using Cochran-Mantel- Haenszel test stratified by baseline 24- hour UP (≥ 1g/24-hour and <2 g/24-hour	
Percent of patients with >50% reduction in 24-hour proteinuria at Week 32	vs. ≥ 2 g/24-hour). The number and percentage of patients who are responders at Week 32 are summarized by treatment arm.	
	The difference in percentages of responders and corresponding 90% CI based on the Wilson score method with continuity correction will be presented.	

 Table 2
 Summary of Analyses for the Secondary Efficacy Endpoints

Endpoint	Statistical Method	Notes
Percent change from baseline in 24-hour proteinuria (g/24- hour) at Week 32	Treatment comparison and estimates will be conducted by a similar MMRM model used for the analysis of primary endpoint. Descriptive statistics will also be generated by treatment arm at each scheduled visit. Geometric Mean (with 90% CI) figures of the ratio to baseline by treatment arm will be plotted as well as individual spaghetti plots.	
Change from baseline in UPCR as measured in a spot urine at Week 32	The change from baseline in log- transformed spot UPCR by visit through Week 36 will be analyzed via a MMRM model. The model includes log- transformed baseline spot UPCR, treatment, visit, and the interaction of treatment and visit. Robust errors [White 1980] will be used to model the within-patient errors. Descriptive statistics will also be generated by treatment arm at each scheduled visit. Geometric Mean (with 90% CI) figures of the ratio to baseline by treatment arm will be plotted as well as individual spaghetti plots.	Scheduled assessments are outlined in the Table 1 (Schedule of Assessments) of the protocol.

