7.3. Exploratory Analyses

Exploratory endpoints will be summarized descriptively by treatment arms during the DB period using mITT Analysis set.

For the slope of eGFR computed for the entire study period, it will also be analyzed by treatment sequence (cemdisiran/cemdisiran, placebo/cemdisiran) using the All Cemdisiran Treated Analysis Set. However, the other exploratory endpoints may be analyzed over the entire study if deemed appropriate. Table 3 summarizes the planned analyses for exploratory endpoints.

Exploratory Endpoint	Statistical Method	Notes
Change from baseline in estimated glomerular filtration rate (eGFR) ¹ at Week 32	Descriptive statistics of eGFR will be presented by visit and treatment arm. Individual patient data will be presented in spaghetti plots. Shift tables of eGFR categories from baseline to post-baseline visits and an overall worst post-baseline will also be presented.	
The slope of eGFR computed for the first 36 weeks using all assessments during the period	The random coefficient model for eGFR will include baseline eGFR, treatment, time (in year), and the interaction of treatment and time as fixed effects and intercept and time as random effects.	The first study drug dosing will be defined as the time reference point t=0 In addition, the slope of eGFR for each subject will be estimated.
The slope of eGFR computed for the entire cemdisiran treatment period including patients who started on placebo in the DB period then switched to cemdisiran in the OLE period, and those started on cemdisiran in the DB period.	The random coefficient model for eGFR will include baseline eGFR, treatment sequence, time (in year), and the interaction of treatment sequence and time as fixed effects and intercept and time as random effects.	This endpoint will be analyzed only at the final analysis using Cemdisiran Treated Analysis set. The first administration of cemdisiran will be defined as the time reference point t=0.
The slope of eGFR during placebo period comparing the slope during OLE for patients who crossed over from placebo to cemdisiran.	The random coefficient model with piecewise regression will include baseline eGFR, time during the placebo treatment and time during the cemdisiran treatment as fixed effects and intercept and times as random effects.	This endpoint will be analyzed only at the final analysis using placebo/cemdisiran treatment sequence group.

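### The double-blind spot UPCR and eGFR analyses use an mITT set that requires a post-baseline 24-hour UPCR, so treated patients with usable data on those endpoints can be dropped

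*SAP*

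**What the plan says.** **Set definition.** Section 4.1 defines mITT as patients who received any study drug and "have baseline and at least one post-baseline 24-hour urine protein creatinine ratio assessment", grouped as randomised. It adds: "The primary population used to evaluate efficacy will be the mITT Population unless stated otherwise".

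**24-hour values analysed.** Section 7.1 lists the double-blind values that enter the primary analysis: "1 valid assessment at week 16 visit and the mean of two valid assessments at baseline and week 32 visit". The model matches this: "The outcome variable is change from baseline in 24-hour UPCR in log-scale at week 16 and week 32 visits".

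**Reuse of the set.**
- Section 7.2: "For secondary endpoints assessed in DB period, the analysis will compare randomized arms (cemdisiran vs. placebo) using the mITT analysis set".
- Section 7.3: "Exploratory endpoints will be summarized descriptively by treatment arms during the DB period using mITT Analysis set".

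**Endpoints that have their own data.** Table 2 gives the spot-urine method, in which the change in log-"transformed spot UPCR by visit through Week 36 will be analyzed via a MMRM model". Table 3 plans a random-coefficient eGFR slope from every assessment in the first 36 weeks, by-visit eGFR statistics, and shift tables that include the worst post-baseline category.

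**Missing data.** Section 5.6 encourages patients who discontinue to keep attending through Week 36. It says that data from before and after stopping treatment will all be used. In the second sensitivity analysis (section 7.1.1), "the missing 24-hour UPCR value will be imputed with the spot UPCR" measured nearest in date. No analysis set is named there.

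**The concern.** Among treated patients, the condition that can exclude is the post-baseline one, because two valid 24-hour collections are already needed for randomisation (section 2.1). Whether a patient later supplies a 24-hour collection is a post-randomisation event, and it could be related to tolerability or response.

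The rule suits the 24-hour UPCR model, where a patient without such a value has nothing to contribute. It does not suit endpoints measured in a spot sample or from serum creatinine. There it discards observed randomised data because a different specimen is missing. With 10 placebo patients, one such loss is noticeable.

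The situation is foreseeable. Section 7.8.1 expects missed and partly completed visits and changes of location. Section 7.8.2 tabulates missing 24-hour UPCR and missing spot UPCR separately.

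**Working it through.** **1. The plan's own precision figure.** Inputs from section 5.1: log SD 0.597, 9 placebo and 18 cemdisiran patients, 90% interval (normal quantile 1.645).

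- SE = 0.597 × √(1/9 + 1/18) = 0.2437
- Half-width = 1.645 × 0.2437 = 0.401; width = 0.802, against the stated 0.80. It reproduces.
- With all 10 and 20 planned patients: SE = 0.2312, half-width 0.380, width 0.761.

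This figure concerns the primary endpoint and is not in dispute. It is based on 27 of the 30 planned patients, but section 5.1 does not say why, so the gap of three cannot be read as a forecast of exclusions from mITT.

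**2. Weight of one exclusion.** Section 2.1 plans 20 cemdisiran and 10 placebo patients: 1/20 = 5% and 1/10 = 10%.

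**3. What the rule costs, endpoint by endpoint (double-blind period).** Consider a treated patient with no post-baseline 24-hour UPCR.

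| Analysis | Could the patient have usable data? | Effect of the mITT rule |
|---|---|---|
| 24-hour UPCR MMRM (primary) | No | None |
| 24-hour UP MMRM | No, the collection is the same | None |
| Spot UPCR MMRM, by visit through Week 36 | Yes | Observed values dropped |
| eGFR slope over 36 weeks | Yes | Observed values dropped |
| eGFR by visit and worst-value shifts | Yes | Observed values dropped |
| Hematuria shift at Week 32 | Only if still attending at Week 32 | Dropped in that case only |
| 24-hour UP responders at Week 32 | No 24-hour value exists | Denominator only |

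**4. Against section 5.6.** That section says all collected data are used. For this patient, the spot UPCR and eGFR values enter no double-blind efficacy comparison. The two sections cannot both apply as written.

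**5. The spot-imputation analysis.** Section 7.1.1 refits the same MMRM after substitution and names no wider set, so mITT applies by default through sections 4.1 and 7.1. On that reading it can repair a missing Week 16 or a missing Week 32 value, but not the case where both are missing. Taking the spot value closest in date also has no distance limit. If early leavers were simply added, an early spot value could stand in for Week 32.

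**6. Precedent within the SAP.** Section 7.4 already uses an endpoint-specific set for pharmacodynamics, defined by C5 sampling, so such sets are not foreign to this plan.

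**The case against.** Several stronger readings are tempting, and the SAP does not support them.

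- **That every efficacy analysis is affected.** Long-term efficacy and the eGFR slope over the cemdisiran period use the All Cemdisiran Treated Set. Its cemdisiran/cemdisiran group keeps patients who stopped during the double-blind period (section 5.2).
- **That stopping treatment excludes a patient.** It does not. Section 5.6 encourages continued visits and uses the later data. Section 4.1 asks for an assessment; it does not say a valid one, and it does not tie it to a scheduled double-blind visit.
- **That Week 16 is certainly the first opportunity.** Section 7.1 lists which values are analysed. The collection schedule is in the protocol, which is not at hand, and an early-termination collection would shrink the problem.
- **That the data are lost.** They remain in the listings, and laboratory safety summaries cover all treated patients.
- **That response rates are inflated.** As a hypothetical case, 9 responders among 20 cemdisiran patients is 45%, but 50% among 18. With 2 of 10 placebo responders (20%), dropping only those two cemdisiran patients moves the difference from 25 to 30 points. Dropping one placebo non-responder instead (2/9 = 22.2%) moves it to 22.8. The direction is not established. The shift also reflects whether missing counts as non-response, a question that arises equally for an mITT patient with a Week 16 value and no Week 32 value.

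It is also fair to say that all comparisons are descriptive (section 5.5) and the primary result does not change. All of these limits stand. None of them explains why spot UPCR and eGFR should depend on a 24-hour collection.

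**Conclusion.** The point holds for the double-blind spot UPCR model, the 36-week eGFR slope and the by-visit and shift summaries of eGFR. Observed randomised data on these endpoints are excluded by a post-randomisation condition that belongs to another measurement, contrary to section 5.6. For hematuria it matters only for patients who attend at Week 32 without any 24-hour value. For the responder endpoints, the question is how to count missing Week 32 values, not a defect of the mITT rule. For the spot-imputation analysis, the SAP leaves the population unstated and the default reading excludes patients with no post-baseline 24-hour UPCR.

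The size is 5% of the cemdisiran arm or 10% of the placebo arm per affected patient. The number affected is unknown and may be zero. The direction of any bias cannot be stated. The conclusion assumes that at least one treated patient has spot UPCR or eGFR data but no post-baseline 24-hour UPCR, which the SAP's own missing-data tables allow for.

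**What to change.** 1. Keep mITT for the 24-hour UPCR and 24-hour UP MMRMs.
2. For double-blind spot UPCR and eGFR, and for hematuria where a value exists, analyse all randomised and treated patients, as randomised, with a baseline and at least one post-baseline value of that endpoint.
3. In section 7.1.1, state that the spot-imputation analysis also includes treated patients with no post-baseline 24-hour UPCR who have a spot UPCR at the missing visit. State that an earlier spot value is not carried forward to Week 32.
4. Optional: add an all-treated responder analysis that counts missing as non-response. This is a supplement, not a correction of the mITT rule.

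The cost is SAP wording and, if item 4 is taken up, an extra responder table. No new data are needed and the primary analysis does not change. Denominators will differ slightly between endpoints and need a footnote.
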